### **1.1.3      *Rationale for Anti-LAG-3 Antibody (BMS-986016) Therapy***

BMS-986016 (relatlimab; these terms are interchangeably used throughout the document) is a fully human antibody specific for human LAG-3 that was isolated from immunized transgenic mice expressing human immunoglobulin genes. It is expressed as an IgG4 isotype antibody that includes a stabilizing hinge mutation (S228P) for attenuated Fc receptor binding in order to reduce or eliminate the possibility of antibody- or complement-mediated target cell killing. BMS-986016 binds to a defined epitope on LAG-3 with high affinity ( $K_d$ , 0.25 to 0.5 nM) and specificity and potently blocks the interaction of LAG-3 with its ligand, [REDACTED] (IC50, 0.7 nM). The antibody exhibits potent in vitro functional activity in reversing LAG-3-mediated inhibition of an antigen-specific murine T cell hybridoma overexpressing human LAG-3 (IC50, 1 nM). In addition, BMS-986016 enhances activation of human T cells in superantigen stimulation assays when added alone or in combination with nivolumab (anti-PD-1 antibody).

### **1.1.5      *Summary***

Combined inhibition of T cell checkpoint molecules, such as CTLA-4, PD-1, and LAG-3, in preclinical models provides synergistic improvement in T cell activity, control of virus replication, and tumor inhibition in animal models. These observations led to the discovery of one of the key signature molecules associated with T cell exhaustion, the negative T cell regulator, LAG-3, and to the development of the antagonistic LAG-3 antibody, BMS-986016.

An initial evaluation of the safety, tolerability, pharmacokinetics (PK), and pharmacodynamics will be conducted with an escalation arm of BMS-986016 monotherapy. It is proposed that this antibody should be considered for the treatment of multiple malignancies in combination with nivolumab (an anti-PD-1 antibody) as a T cell-core therapy with the aim to: 1) increase the number, type, and DORs in tumors known to respond to T cell checkpoint inhibitors; 2) rescue an adaptive response where patients are refractory to T cell checkpoint inhibitors and have progressed clinically; and/or 3) enhance the antitumor immunity in malignancies associated with chronic viral infections (eg, HPV, EBV, HCV, HBV, etc).

### **1.1.6      *Rationale for Part D Expansion***

As of the cutoff date of 15-Jun-2017, preliminary proof-of-concept efficacy has been revealed in the Part C combination treatment expansion cohort of advanced melanoma with prior treatment with anti-PD-1/PD-L1. All subjects were treated with BMS-986016 80 mg + nivolumab 240 mg every 2 weeks (Q2W). The overall ORR was 11.5% (7/61 response evaluable), with a disease control rate (DCR) of 49%. Biomarker analyses suggested that subjects whose TIL expressed more LAG-3 had a higher response rate, with a greater than 3-fold increase in ORR observed in subjects with evidence of LAG-3 expression in at least 1% of nucleated cells within the tumor margin,

compared with less than 1% LAG-3 expression (18.2% [6/33] and 5.0% [1/20], respectively). PD-L1 expression did not appear to enrich for response. The treatment group had the following characteristics: 1) most subjects had M1C disease (68%), 2) the cohort was heavily pretreated (77% with 2 or more prior therapies and 57% with prior anti-CTLA-4 therapy), 3) all subjects had progressed while receiving anti-PD-1/PD-L1, and 4) progressive disease (PD) was the best response to prior anti-PD-1/PD-L1 in 46% of subjects. Overall, anti-LAG-3 (BMS-986016) in combination with nivolumab demonstrated encouraging initial efficacy with a safety profile similar to nivolumab monotherapy.

Based on initial efficacy signal in advanced melanoma subjects who progressed on anti-PD-1/PD-L1 therapy, additional subjects in this subset population for further clinical testing are justified. Assessment in this population will be extended in 2 subparts: Part D1 and D2. D1 will test the combination in a focused eligibility population, whereas D2 will allow assessment in a broader population under expanded eligibility criteria.

Given the improved response rate in subjects whose tumor-associated immune cells express more LAG-3, efficacy analysis in Part D1 will be the primary focus. Subjects whose tumors are LAG-3 negative will also be evaluated to determine the role of LAG-3 expression on the antitumor activity of BMS-986016. Part D2 will explore safety and efficacy in a broader patient population, including those with Eastern Cooperative Oncology Group performance status (ECOG PS) up to 2 and among those with a more diverse set of prior therapies.

### **1.1.7      *Rationale for Part E (Melanoma Expansion)***

At the time of incorporation of Part E into this protocol, the majority of the melanoma patients evaluated within the BMS-986016 clinical development program have been treated with the BMS-986016 160 mg + nivolumab 480 mg every 4 weeks (Q4W) dosing regimen or BMS-986016 80 mg + nivolumab 240 mg Q2W dosing regimen. Although preliminary evidence indicates that BMS-986016 160 mg + nivolumab 480 mg Q4W is a reasonable dose, it is possible that higher doses may produce additional clinical benefit for melanoma participants. Accordingly, in an effort to more fully elucidate the dose-response curve in melanoma participants, Part E of this protocol includes the evaluation of the BMS-986016 480 mg + nivolumab 480 mg Q4W dosing regimen.

The BMS-986016 480 mg + nivolumab 480 mg Q4W dosing regimen has been evaluated in Part B (Dose Escalation with DLT Criteria) of this study. Seven (7) subjects were treated, and no DLTs were observed. Accordingly, the BMS-986016 480 mg + nivolumab 480 mg Q4W dosing regimen was determined by the Principal Investigators conducting Part B to have an acceptable safety profile that warranted dose escalation to the BMS-986016 960 mg + nivolumab 480 mg Q4W dosing regimen. Subsequently, the BMS-986016 960 mg + nivolumab 480 mg Q4W dosing regimen was evaluated. Three (3) subjects were treated, and there were no DLTs. Accordingly, the BMS-986016 960 mg + nivolumab 480 mg Q4W dosing regimen was determined by the Principal Investigators conducting Part B to have an acceptable safety profile that warranted dose escalation to the BMS-986016 1440 mg + nivolumab 480 mg Q4W dosing regimen.

Melanoma participants who experienced disease progression on anti-PD-1 therapy and melanoma participants with previously untreated metastatic or unresectable disease will be included in Part

E. More specifically, these 2 participant cohorts are defined, respectively, as an advanced melanoma participant who has progressed (radiologically confirmed) on prior anti-PD-1 therapy within 3 months of the last anti-PD-1 dose and an advanced melanoma participant who has not received prior systemic anticancer therapy for unresectable or metastatic melanoma. Please refer to [Section 3.3](#) of this protocol for complete definitions of these participant cohorts and details on applicable inclusion/exclusion criteria.

In participants who experienced disease progression on prior anti-PD-1 therapy, only the BMS-986016 480 mg + nivolumab 480 mg Q4W dosing regimen will be evaluated. In the cohort of participants who have not received prior systemic anticancer therapy for unresectable or metastatic melanoma, both the BMS-986016 160 mg + nivolumab 480 mg Q4W and the BMS-986016 480 mg + nivolumab 480 mg Q4W dosing regimens will be evaluated.

The rationale for limiting the cohort of participants who experienced disease progression on anti-PD-1 therapy cohort to only the BMS-986016 480 mg + nivolumab 480 mg Q4W dosing regimen is that there is substantial clinical experience in melanoma participants who experienced disease progression on anti-PD-1 therapy with the BMS-986016 160 mg + nivolumab 480 mg Q4W dosing regimen. That substantial clinical experience will be used as a historical control for the purpose of elucidating the dose-response curve in this cohort of melanoma subjects. For the cohort of participants who have not received prior systemic anticancer therapy for unresectable or metastatic melanoma, where the clinical experience is more limited, participants will be randomized to 1 of the 2 dosing regimens.

#### **1.1.8      *Parts C, D, and E (Melanoma Only) Rationale for Inclusion of Adolescents***

Patients under 18 years of age have often been excluded from adult oncology trials because of safety or regulatory concerns; a practice that leads to delays in pediatric studies. Separate adult and pediatric cancer centers, distinct cooperative research groups, and oncologists specializing in different populations do not often conduct unified adult–pediatric clinical trials or drug-development programs.

Although rare, the incidence of childhood and adolescent melanoma in the United States has been increasing in the past 35 years. This trend is most prominent in the adolescent age range, specifically those 15 to 19 years of age. Single-center and industry-sponsored trials often exclude advanced melanoma adolescent patients for historical or empiric reasons. A recent genomic analysis of pediatric melanoma demonstrates that conventional melanoma in children and adolescents shares many of the genomic features that have been described in adult melanoma, including BRAF mutations. The abstract of this genomic analysis advocated for the opportunity for pediatric patients to be enrolled in pharmaceutically sponsored trials that incorporate novel agents. Many pediatric subjects who are diagnosed with melanoma are referred to and treated by medical oncologists vs pediatric oncologists, due to divergent expertise in the field.

### **1.1.9 Rationale for Dose Selection**

CA224020 currently consists of 6 parts. Part A and Part B consist of a 3 + 3 + 3 dose escalation design and, implemented in site-specific amendment #15 (dated 13 August 2018) and superseding the 3 + 3 + 3 dose escalation design, the Bayesian Logistic Regression Model (BLRM)-Copula design, with BMS-986016 administered as a single agent (Part A) or in combination with nivolumab as sequential infusion (Part B) in subjects with advanced solid tumors. Part A1 consists of expansion cohorts of approximately 6 to 12 subjects in each disease-restricted population, with BMS-986016 monotherapy. Part C consists of expansion cohorts of approximately 25 to 40 subjects each in disease-restricted populations (and further expansion of up to approximately 90 to 120 subjects in selected cohorts based upon safety and efficacy profiles), with BMS-986016 administered in combination with nivolumab as sequential infusions. Part D consists of advanced melanoma subjects with progression on prior anti-PD-1 therapy enrolled into 2 subgroups based upon eligibility criteria. Part E consists of both melanoma participants who experienced disease progression on prior anti-PD-1 therapy and melanoma participants who have not received prior systemic anticancer therapy for unresectable or metastatic melanoma. The sequential infusion of BMS-986016 and nivolumab will be administered in Parts A, A1, B and C. In Part D, subjects will be administered BMS-986016 and nivolumab coadministration or BMS-986213 (fixed-dose combination [FDC] relatlimab/nivolumab at a 1:3 ratio in a single vial). In Part E, subjects will be administered BMS-986016 and nivolumab as a coadministration. See [Section 4.1.1](#) for details.

#### **1.1.9.1 Rationale for Flat Dosing**

Therapeutic mAbs doses have been routinely calculated on a body size basis with a perception that this approach may reduce intersubject variability in drug exposure compared with a flat dose approach. However, recent analyses of marketed and experimental mAbs have demonstrated that body weight-based dosing did not always offer advantages over flat dosing in reducing exposure variability. Since the magnitude of the impact of body weight on the human PK of BMS-986016 is not yet determined and it is unknown if body size-based dosing would increase or decrease intersubject variability, this study will utilize a flat dose escalation and expansion since it is the simpler of the 2 approaches and may result in fewer dosing errors. The impact of body weight on the PK of nivolumab is small, and the dose-response relationship is relatively shallow near the 3-mg/kg dose level, indicating that nivolumab can also be administered as a flat dose in combination with BMS-986016 in this study.

Flat doses for this study have been normalized for an average 80-kg adult cancer patient. A dataset from the nivolumab program used for preliminary population PK contained 325 subjects with a median weight of 81 kg. This value aligns well with a study by Bai et al, which found a median weight of 78 kg in 2519 adult patients with rheumatoid arthritis, breast cancer, colorectal cancer, NSCLC, ovarian cancer, and non-Hodgkin's lymphoma.

Additionally, BMS-986016 flat dose of 20 to 800 mg as monotherapy and up to 480 mg in combination with nivolumab (both given Q2W) has been studied across the 40 to 120 kg weight range in adults.

### **1.1.9.2 Part A — BMS-986016 Dose**

The first-in-human dose selected for this study is based on all available nonclinical data.

To balance the potential for pharmacologic activity and reasonable safety in this cancer patient population, a dose of 20 mg (0.25 mg/kg) was selected as the starting dose in monotherapy (Arm A). This dose is less than 1/10 of the human equivalent dose (HED) of the no-observed-adverse-effect level (NOAEL) in the 4-week toxicity study (636 mg; 8.0 mg/kg) and is below the HED after a linear adjustment of the NOAEL target exposure for the highest affinity difference estimate of 265-fold (24 mg; 0.30 mg/kg) between activated human and cynomolgus T cells. No additional safety factor was added to the affinity-adjusted calculation because a linear adjustment is expected to be a conservative approach. Based on the model from the mouse efficacy data, this dose has the potential to have antitumor activity in humans. The calculated safety multiple for the 20-mg (0.25 mg/kg) dose is 315-fold based on the NOAEL of 100 mg/kg/week in the 4-week repeat-dose monkey study without accounting for affinity differences. In addition, a staggered dosing (sentinel subject) approach will be used in the first dose cohort, as described in [Section 3.1.1.1](#). The top dose of 800 mg (10 mg/kg) is projected to have the potential for 71% to 179% TGI from the most sensitive model in mouse.

### **1.1.9.3 Part B — BMS-986016 Dose (Applies to Only a Subset of Sites 1-6)**

*Administrative Note: Only a limited number of sites are conducting Part B of this protocol. Each investigational site that is participating in Part B will receive an administrative letter from BMS confirming their participation in Part B that can be submitted to their respective Institutional Review Board (IRB) or Independent Ethics Committee (IEC).*

The starting doses for Part B were selected based on all nonclinical data available from studies of the combination and BMS-986016 monotherapy and on emerging clinical safety and PK data from Part A monotherapy. In the 4-week repeated-dose Good Laboratory Practice (GLP) toxicology study, a dose of 100 mg/kg/week of BMS-986016 + 50 mg/kg/week nivolumab was considered the severely toxic dose in 10% of the animals (STD10; refer to [Section 1.4.1.2](#)). The same approach to identifying HEDs as described for monotherapy was used. Using a linear adjustment of the STD10 for a 265-fold affinity difference results in a dose of 20 mg (~0.3 mg/kg).

Pharmacokinetic data from Part A monotherapy suggested that subjects treated at 20 mg BMS-986016 (flat dose) have significant lower exposure compare to exposure associated with toxicity in the GLP toxicology study with 100 mg/kg/week of BMS-986016 + 50 mg/kg/week nivolumab in cynomolgus monkey. Furthermore, BMS-986016 monotherapy was well tolerated in subjects treated with up to 800 mg BMS-986016 (flat dose) in Part A. The only high-grade related toxicity was an asymptomatic, self-limited, G3 lipase elevation in 1 subject treated at 20 mg flat dose. Therefore, the proposed starting dose for BMS-986016 in combination with nivolumab in Part B was 20 mg (~0.3 mg/kg) given Q2W. This dose cohort was initiated after the decision was made to escalate to the third dose cohort in Part A (monotherapy) in accordance with the dose escalation rules. Delaying initiation of the first dose cohort in Part B until after evaluation of the first 2 cohorts in Part A (ie, up to 80 mg flat dose) provided additional clinical safety data with single-agent BMS-986016 at doses 4-fold higher than the 20-mg dose prior to administration.

of the combination. In addition, a staggered dosing (sentinel subject) approach will be used in the first dose cohort as described in [Section 3.1.1.2](#).

While the majority of assessments in this study have been and will be conducted using Q2W dosing, a Q4W dosing regimen will also be assessed in this study. Specifically, extending the dosing interval to Q4W provides numerous benefits to patients, including increased flexibility between clinical visits compared with Q2W.

The initial Q4W dose escalation (3 + 3 + 3 design) is as follows: 160, 240, and 320 mg. Upon completion of safety evaluation from these initial dose escalations, additional higher doses, including 480, 960, 1440, and 1600 mg Q4W, will be evaluated to assess a maximum tolerated dose (MTD). Proposed higher doses of 480 to 1600 mg Q4W are predicted to provide a dose-proportional increase in exposure by following linear PK. The top dose of 1600 mg is predicted to provide steady state average concentrations similar (< 5%) to the maximum administered dose (MAD) of 800 mg Q2W in human and steady state maximum observed concentration (Cmaxss) well below the observed exposure at the NOAEL dose in the 3-month repeat-dose toxicity studies in cynomolgus monkeys. [REDACTED]

[REDACTED] [\(Section 1.4.1.4\)](#). The increment of subsequent dose levels after the initial 320-mg dose level can be modified based on the BLRM-Copula recommendation.

#### **1.1.9.4 Parts B, C — Nivolumab and Combination Dosing - Sequential Infusion**

As mentioned previously, a dose of 100 mg/kg/week of BMS-986016 + 50 mg/kg/week nivolumab was considered the STD10 in the 4-week toxicity study. Known human nivolumab PK parameters were used to calculate the HED. The same approach to identifying HEDs as described for monotherapy was used. With an added 10-fold safety factor, the maximum recommended starting dose based on the STD10 is 320 mg (~4 mg/kg) in humans. The starting nivolumab dose for subjects in Part B is 80 mg (1 mg/kg) Q2W. All subsequent cohorts on Q2W schedule are planned to be administered 240 mg of nivolumab, which is equivalent to the well-tolerated global nivolumab monotherapy Phase 3 dose 3 mg/kg Q2W. Most recently, the nivolumab dosage regimen was modified to a flat 240 mg Q2W as monotherapy for melanoma, NSCLC, and RCC in the US. [USPI ([Appendix 1](#))] In Part B with Q2W dose escalation cohorts, doses will be administered sequentially as nivolumab intravenous (IV) infusion over 60 minutes, followed by BMS-986016 infusion over 60 minutes.

In Part B, for the less frequent dosing regimen (Q4W), nivolumab dose of 480 mg will be administered in combination with BMS-986016. Based on PK modeling and simulations, while 480 mg Q4W is predicted to provide greater (approximately 40%) maximum steady state concentrations and lower (approximately 20%) steady state trough concentrations, these exposures are predicted to be within the exposure ranges observed at doses up to 10 mg/kg Q2W used in the Phase 1 nivolumab clinical program and are not considered to put subjects at increased risk. Similar to the nivolumab Q2W dosing monotherapy regimen, the exposures predicted following administration of nivolumab 480 mg Q4W are on the flat part of the exposure-response curves for previously investigated tumors (ie, melanoma and NSCLC) and are not predicted to affect efficacy.

Based on these data, nivolumab 480 mg Q4W is expected to have similar efficacy and safety profiles to nivolumab 240 mg or 3 mg/kg Q2W.

The dosing and schedule for subjects in Part C will be agreed upon by Investigators and the Sponsor based upon dosing shown to be safe in Part B. In Part B and Part C, the sequential infusion of both drugs will start with nivolumab administration first, followed by infusion of BMS-986016. Based upon review of the available safety, PK, [REDACTED]

[REDACTED], Part C expansions commenced at combination dosing of 80 mg BMS-986016 and 240 mg nivolumab Q2W (see Section 1.4.1.4.2 of this protocol and the BMS-986016 Investigator Brochure [IB]). The planned treatment for the bladder immuno-oncology (IO)-naive cohort will be sequential dosing of 160 mg BMS-986016 with 480 mg nivolumab Q4W. However, if 160 mg BMS-986016 with 480 mg nivolumab Q4W is deemed not safe, then the 80 mg BMS-986016 with 240 mg nivolumab Q2W regimen will be given.

#### **1.1.9.5 Rationale for 30-minute Nivolumab Infusion**

Administration of nivolumab using a 30-minute infusion time has been evaluated in subjects with cancer and was shown to be safe.

#### **1.1.9.6 Part D: Coadministration or Fixed-dose Combination**

In Part D, advanced melanoma subjects with progression on prior anti-PD-1 therapy will be enrolled in 2 subgroups based on eligibility criteria. If eligible for the focused D1 group, subjects will be randomized across 3 arms (see [Section 3.1.2.5](#) for details):

Arm 1: BMS-986016 80 mg + nivolumab 240 mg given by coadministration Q2W

Arm 2: BMS-986016 160 mg + nivolumab 480 mg given by coadministration Q4W

Arm 3: BMS-986213 (relatlimab 160 mg/nivolumab 480 mg) given Q4W; BMS-986213 contains both relatlimab and nivolumab in the same solution at a ratio of 1:3

The expanded eligibility Part D2 cohort will all be treated using the more convenient Q4W dosing in 2 different dose combinations: 160 mg BMS-986016 + 480 mg of nivolumab and subsequently 240 mg BMS-986016 + 480 mg of nivolumab (described in [Section 3.1](#)). The combination treatment in Part D2 will be coadministered.

The less frequent dosing regimen given Q4W was selected based on model predicted PK, [REDACTED] and acceptable safety profile up to BMS-986016 160 mg + nivolumab 240 mg given Q2W in this study and ongoing study CA224022. BMS-986016 160 mg + nivolumab 480 mg Q4W is predicted to provide similar steady state BMS-986016 exposure (ie, steady state average concentration [Cavgss]) [REDACTED] comparable to the levels achieved when BMS-986016 80 mg + nivolumab 240 is dosed Q2W. BMS-986016 240 mg + nivolumab 480 mg Q4W is predicted to maintain steady state exposure (ie, Cavgss) [REDACTED] below the levels achieved when BMS-986016 160 mg + nivolumab 240 mg is given Q2W, a dose shown to be tolerable in Part B. In addition, confirmation of the predicted safety of BMS-986016 240 mg + nivolumab 480 mg Q4W is ongoing, and employment of this dose will commence upon appropriate safety assessment in Part B. If BMS-986016 240 mg + nivolumab 480 mg Q4W is

considered toxic based on [Section 3.1.2.3](#), then further expansion will resume at BMS-986016 160 mg + nivolumab 240 mg Q2W.

**For coadministration treatments, BMS-986016 and nivolumab will be mixed in same infusion bag and will be administered over approximately 60 minutes.** The decrease in infusion time will allow for increased convenience for patients, doctors, nursing staff, other health-care staff members, and pharmacists. Key advantages of a coadministration of this combination are as follows:

Patients benefit from reduced infusion time and less time in the clinic and/or doctor's office

Increased ease of administration

Pharmacists require less time in preparation of the IV solution to be administered to the patient

For the FDC drug product (BMS-986213) treatment, BMS-986213 will be administered over approximately 60 minutes. The advantages of the use of a single-vial drug product include easier and more rapid administration and infusion preparation, as well as decreased opportunity for dosing and administration errors.

Although coadministration and treatment with the FDC drug product (BMS-986213) would result in overlapping time of maximum observed concentration (Tmax) for BMS-986016 and nivolumab, the PK and exposure of both agent will be the same as when administered sequentially. Therefore, sequential administration vs coadministration (ie, single infusion bag) vs BMS-986213 (FDC) administration is not expected to impact the overall safety profile.

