### **All Cohort Expansion Parts (Parts A1, C, D, and E)**

Continuous evaluation of toxicity events in the cohort expansions will be performed throughout enrollment in the expansion cohorts. If, at any time, the aggregate rate of treatment-related toxicities meeting DLT criteria exceeds 33% across all subjects treated in any of these cohort expansions, the findings will be discussed, and further enrollment must be interrupted in that particular cohort and other relevant cohorts. Depending on the nature and grade of the toxicity, and after assessing the benefit-risk ratio, a new dose(s) for all cohorts may be initiated at a previously tested lower dose level or at a dose level intermediate to previously tested lower dose levels.

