### **3.1.2.3 *All Cohort Expansion Parts (A1, C, D, and E)***

Continuous evaluation of toxicity events in the cohort expansions will be performed throughout enrollment in the expansion cohorts. **Not applicable as per Protocol Amendment 14:** Safety conference calls with the BMS Medical Monitor, Investigators, and representatives of the Sponsor are being held regularly during conduct of the study. In addition, separate BMS Medical Safety Teams routinely review safety signals across the BMS-986016 and nivolumab programs. If, at any time, the aggregate rate of treatment-related toxicities meeting DLT criteria exceeds 33% across all subjects treated in any of these cohort expansions, the findings will be discussed and further enrollment must be interrupted in that particular cohort and other relevant cohorts. Depending on the nature and grade of the toxicity and after assessing the benefit-risk ratio, a new dose(s) for all

cohorts may be initiated at a previously tested lower dose level or at a dose level intermediate to previously tested lower dose levels.

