### **8.1.4.3 Melanoma Prior IO Expanded Eligibility Expansion (Part D2)**

Part D2 will have an expanded eligibility criteria with 2 cohorts in sequence: 160 mg BMS-986016 with 480 mg nivolumab Q4W and 240 mg BMS-986016 with 480 mg nivolumab Q4W. Subjects in Part D2 on average will have a worse performance status and be more heavily treated. Approximately 30 subjects will be initially treated with 160 mg BMS-986016 with 480 mg

nivolumab Q4W. Once this dose level is deemed safe, approximately up to 220 additional subjects will be treated with either 160 mg BMS-986016 with 480 mg or 240 mg BMS-986016 with 480 mg nivolumab Q4W to establish safety and efficacy in this broader group of melanoma patients. With 30 subjects, there is approximately 96% chance to observe at least 1 occurrence of any AE that would occur with a 10% incidence in the population from which the sample is drawn. With 250 subjects, there is approximately 92% chance to observe at least 1 occurrence of any AE that would occur with a 1% incidence in the population from which the sample is drawn. Safety and efficacy data will be collected as in the other cohorts, and the data will be used as supportive evidence of safety and efficacy of the combination therapy.

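### Section 1.1.9.6 answers toxicity at 240/480 mg Q4W with 160/240 mg Q2W, a regimen it predicts to give higher average relatlimab exposure, while Section 3.1.2.3 speaks of a lower dose level and does not define it

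*Combined protocol and SAP*

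**What the plan says.** Section 1.1.9.6 gives the dose rationale for Part D. It predicts that relatlimab 240 mg + nivolumab 480 mg Q4W will hold steady-state average relatlimab concentration "below the levels achieved when BMS-986016 160 mg + nivolumab 240 mg is given Q2W, a dose shown to be tolerable in Part B". Part of that sentence is redacted, but the direction can be read. Shortly afterwards the section states what happens if 240/480 Q4W is considered toxic on the basis of Section 3.1.2.3: "then further expansion will resume at BMS-986016 160 mg + nivolumab 240 mg Q2W".

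Section 3.1.2.3 interrupts further enrollment if "the aggregate rate of treatment-related toxicities meeting DLT criteria exceeds 33% across all subjects treated in any of these cohort expansions". Then, depending on the toxicity and the benefit-risk assessment, new dosing for all "cohorts may be initiated at a previously tested lower dose level or at a dose level intermediate to" previously tested lower ones. The synopsis, under All Cohort Expansion Parts, repeats the rule: "a new dose(s) for all cohorts may be initiated at a previously tested lower dose level or at a dose level intermediate to" such levels. Neither place says whether a dose level is ranked by dose per infusion, dose over time or exposure.

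Section 8.1.4.3 describes Part D2 as "2 cohorts in sequence: 160 mg BMS-986016 with 480 mg nivolumab Q4W and 240 mg BMS-986016 with 480 mg nivolumab Q4W". Section 1.1.9.6 likewise says that all of Part D2 is dosed Q4W. Part D1 uses 80/240 Q2W, 160/480 Q4W and the fixed-dose product at 160/480 Q4W, so 160/240 Q2W is not a listed regimen anywhere in Part D.

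**The concern.** A toxicity rule is normally expected to lower exposure to the agent under suspicion, or at least not to raise it. Here the definite instruction in Section 1.1.9.6 leads from a regimen judged too toxic to one that the same section ranks above it on average relatlimab exposure. The section cites Section 3.1.2.3 as the trigger, yet the response it names fits that section only under one of several possible readings of a lower dose level.

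At stake is the regimen for subjects enrolled into Part D2 after such a switch, and whether two readers of the protocol would act alike. There is also a mismatch of design: the fallback would put a Q2W regimen into a part described throughout as Q4W. The dosing rows of Table 5.1-2 have no Q2W entry for Part D2, and the weight-based doses for adolescents under 40 kg in Section 1.1.9.8 include none corresponding to 160/240 Q2W.

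**Working it through.** The plan gives no figure for the size of the exposure difference, so there is none to reproduce. The direction is the plan's own; the size below is derived.

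**Dose over 4 weeks** (doses from Section 1.1.9.6; dose per 4 weeks = dose per infusion × 28 / interval in days)

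| | 240/480 Q4W | 160/240 Q2W | Ratio, fallback to 240/480 |
|---|---|---|---|
| Relatlimab per infusion | 240 mg | 160 mg | 0.67 |
| Nivolumab per infusion | 480 mg | 240 mg | 0.50 |
| Relatlimab per 4 weeks | 240 × 28/28 = 240 mg | 160 × 28/14 = 320 mg | 1.33 |
| Nivolumab per 4 weeks | 480 mg | 240 × 2 = 480 mg | 1.00 |

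Under linear pharmacokinetics, average steady-state concentration is proportional to dose divided by interval. The fallback's average relatlimab concentration would then be about 320/240 = 1.33 times that of the regimen judged toxic. This agrees in direction with Section 1.1.9.6.

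**Does this scaling match the plan's own comparisons?**
- Section 1.1.9.6 treats 160 mg Q4W and 80 mg Q2W as similar in average exposure. Both are 160 mg per 4 weeks.
- Section 1.1.9.3 predicts 1600 mg Q4W to be within 5% of 800 mg Q2W on average concentration. Both are 1600 mg per 4 weeks.

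**Side check on peak and trough** (an assumption, not the plan's model). Take a one-compartment bolus model with half-life h days, and let x = 2^(−14/h). At steady state, fallback relative to 240 mg Q4W:
- peak ratio = (160/240) × (1 + x)
- trough ratio = (160/240) × (1 + 1/x)

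The superseded contraception criterion in Section 3.3.1 equates 5 half-lives with 135 days, so h = 135/5 = 27 days.

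| h (days) | Peak ratio | Trough ratio |
|---|---|---|
| 10 | 0.92 | 2.43 |
| 14 | 1.00 | 2.00 |
| 20 | 1.08 | 1.75 |
| 27 | 1.13 | 1.62 |
| 30 | 1.15 | 1.59 |

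The average and trough are higher with the fallback throughout this range. The steady-state peak is lower only for half-lives under 14 days. The dose per infusion, and with it the peak after the first dose, is lower in every case.

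**Conclusion of the check.** By dose per infusion, 160/240 Q2W is a lower level for both drugs. By relatlimab per 4 weeks, or by the average exposure that Section 1.1.9.6 uses, it is a higher one. Section 3.1.2.3 and the synopsis do not choose between these measures.

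**The case against.** The best defence is the per-infusion reading. Table 3.1.1.2-1 lists Part B levels in mg per infusion, and there 160/240 is below 240/480 for both drugs. It was also tested, as the intermediate Q2W cohort, and Section 1.1.9.6 calls it tolerable, whereas the safety of 240/480 Q4W was at that point only predicted. Returning to a regimen with clinical experience is a coherent choice. Section 1.1.9.4 has a similar pattern for the bladder cohort: if 160/480 Q4W is unsafe, treatment is 80/240 Q2W.

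This softens the conflict but does not remove it. Section 1.1.9.6 compares the two regimens by average concentration, not per infusion. Tolerability in Part B shows that a regimen was tested; it does not make it lower than one later judged toxic. The bladder fallback leaves relatlimab at 160 mg per 4 weeks under both regimens, while this one raises it.

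Other points on that side stand. Section 3.1.2.3 is permissive, and Section 3.1.2.5 lets the investigators and sponsor alter Part D cohort dosing as data emerge. Section 8.1.4.3 allows the additional Part D2 subjects to receive either of the two Q4W regimens. The Q2W fallback appears only in the rationale, not in Section 3.1.2.5 or 8.1.4.3. Appendix 7 (rationale for Protocol Amendment 14) records that enrollment closed on 30-Jul-2021, so no expansion can now resume.

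Three stronger readings that a reader might infer are not supported:
- **That Section 3.1.2.3 permits nothing but a lower level, so the fallback breaches it.** The section says that a new dose may be started at such a level; it does not forbid alternatives.
- **That subjects already on treatment would be moved to higher exposure.** Both passages concern further enrollment. Section 3.1.2.5 rules out dose adjustment for individual subjects, and Section 4.3.1.2 bars reduction within a subject except where a dose is found to exceed the MTD.
- **That the Part D2 safety-precision statement would fail.** The 92% in Section 8.1.4.3 is 1 − 0.99^250. It depends only on the number of subjects and already pools two doses.

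**Conclusion.** The inconsistency is real. Section 1.1.9.6 directs expansion, after toxicity at 240/480 Q4W, to a regimen that it predicts to give higher average relatlimab exposure. Section 3.1.2.3, which it cites, speaks of a lower dose level without defining the measure. The derived size is 320 against 240 mg of relatlimab per 4 weeks, about 33% more, with nivolumab unchanged at 480 mg.

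The direction comes from the protocol. The 33% assumes exposure proportional to dose rate and is approximate, because Section 1.4.1.4.1 describes a nonlinear and time-varying clearance. The peak and trough ratios rest on a simplified model and are illustrative only.

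The fallback also lies outside the Q4W-only description of Part D2. The point bears on subsequently enrolled subjects, and with enrollment closed its practical effect is limited to the clarity of the protocol record. It remains worth correcting: this is a safety rule, and the sentence stands in the current text without being marked as no longer applicable, as superseded text is elsewhere. None of this shows which regimen, or which of the passages, is right.

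**What to change.** Reconcile Section 1.1.9.6 with Section 3.1.2.3, its counterpart in the synopsis, and the Part D2 descriptions in Sections 1.1.9.6 and 8.1.4.3, so that they give one consistent response to toxicity at 240/480 Q4W. State in Section 3.1.2.3 and the synopsis the measure by which a lower dose level is judged: dose per infusion, dose per 4 weeks, or an exposure metric such as average or peak concentration. If the conditional sentence no longer applies because enrollment is closed, mark it so in the way used for other superseded text.

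Which regimen is named and which passage prevails are decisions for the sponsor and investigators. The cost is a sentence or two of protocol text, with no change to sample size or analysis.
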